#### Cut off point:

When using an ANRQ cut-off point of 31 or more (equal costs of errors), we obtained a sensitivity of 0.35, specificity of 0.89 and a positive predictive value of 0.43. A score of 23 or more gave approximately equal sensitivity (0.62) and specificity (0.64) and a positive predictive value of 0.30.

#### Test re-test

A test-retest technique was carried out using a randomly selected sample of 21 ante-natal mothers to assess the ANRQ reliability. Out of these 21 respondents, 16 (76.2%) had valid responses for the analysis. ANRQ was administered twice allowing a one-week period between the first and second administration, followed by an item analysis of the two sets of responses. The English version was first administered, followed by the Maltese version. Cohen's kappa was used to measure inter-rater agreement for the binary (Yes-No) questions and its extension, Cohen's weighted kappa was used as a measure of inter-rater agreement for ordinal scales.

The percentage agreement of ANRQ ranged from 57.1% to 100.0%, with all p-values for each question resulted to be less than 0.05 level of significance, indicating sufficient test-retest reliability (Table 3).

Finally, the ANRQ total score was calculated for both English and Maltese versions. An intraclass correlation was used to check for the correlation (agreement) between the Maltese and English version. The estimated reliability between the Maltese and English versions was 0.877, with 95% Confidence Interval (0.691, 0.955), which indicates an excellent reliability. Moreover, the F-statistic value is 15.262 with degrees of freedom (df1 and df2) equal to 15 and 16, respectively. One can note that the p-value is <0.001. Since the resulting p-value is less than 0.05, this indicates that there is a statistically significant agreement between the Maltese and English versions for ANRQ total score - ICC = 0.877 (95% CI, 0.691 to 0.955), F(15,16) = 15.262, p < 0.00.

Question	Percentage of Agreement	Kappa Value	P-value	Result
Q1. When you were growing up, did you feel your mother was emotionally supportive of you?	100.0%	1.000	<0.001	Statistically significant
Q2a. Have you ever had 2 weeks or more when you felt particularly worried, miserable, or depressed?	93.8%	0.818	<0.001	Statistically significant
Q2b. Do you have any other history of mental health problems?	100.0%	1.000	<0.001	Statistically significant
Q2c. Seriously interfere with your work and your relationships with friends and family?	69.2%	0.527	<0.001	Statistically significant
Q2d. Lead you to seek professional help?	100.0%	1.000	<0.001	Statistically significant
Q2e. Did you take tablets/herbal medicine?	100.0%	1.000	<0.001	Statistically significant
Q3. Is your relationship with your partner an emotionally supportive one?	93.8%	0.923	<0.001	Statistically significant
Q4a. Have you had any stresses, major changes or losses in the last 12 months?	87.5%	0.750	0.002	Statistically significant
Q4b. How distressed were you by these stresses, changes or losses?	57.1%	0.720	0.004	Statistically significant
Q5. Would you generally consider yourself a worrier?	62.5%	0.460	0.010	Statistically significant
Q6. In general, do you become upset if you do not have order in your life (e.g. regular time table, a tidy house)?	81.3%	0.726	<0.001	Statistically significant
Q7. Do you feel you have people you can depend on for support with your baby?	75.0%	0.701	<0.001	Statistically significant
Q8. Were you emotionally abused when you were growing up?	100.0%	1.000	<0.001	Statistically significant
Q9. Have you ever been abused sexually or physically?	100.0%	1.000	<0.001	Statistically significant

Table 3: Test-retest results of ANRQ

#### **Ethics**

The Ethics Application for the study was approved by FREC and UREC. UREC-DP2011001SWB - 6543\_05102020\_[name]

#### **Analytic Methods**

The analysis of the data will be conducted by the Statistical Package for the Social Sciences, IBM SPSS 28 and R Studio.

RCT 1 the antenatal period: Provide the evidence as to whether an intervention to support mothers who are suffering from anxiety or depression during the antenatal period will make a significant difference to these mothers viz a viz the parents in the control group

Baseline characteristics will be compared between the two groups (Intervention/Control) to observe whether the two groups showed any demographic differences. To assess baseline participant differences, binominal logistic regression will be used to test for demographic differences across the two study groups – the intervention group and the control group. Any baseline demographic factor that differed between the two groups at p < 0.10 will be included as a potentially confounding variable in follow-up models testing for the effect of the intervention. Effect sizes will be given in terms of odds ratios for analyses using binomial logistic regression, , with 1 meaning no difference, values under 1 meaning less likely, and values over 1 meaning more likely to occur in the intervention compared to control group. However, this approach will be feasible if there is enough detail to conduct such analysis for certain demographic variables. If such problem arises, alternatively, a Chi-Square test of association will be carried out by selected demographic variables to see whether the two groups showed any demographic differences. The null hypothesis specifies that there is no association between the two variables and will be accepted if the p-value exceeds the 0.05 level of significance. The effect size for the chi-square test was measured using Cramer's V.

Pre-and post-means, medians, and standard deviations for all the measures, namely the GAD-7, EPDS and R-DAS will be compared and analysed between the respective groups, namely for the intervention and control group participants. Descriptive measures will also be presented visually using boxplots comparing pre-and post- test scores for each group. The paired samples t-test can be used to compare the mean scores of the pre-and post-sessions of both groups. If the differences of the pre-post measures deviate from the normality assumption, the Wilcoxon Signed-Ranks test should then be used to compare the scores between the pre-post periods for both intervention and control groups. The change of the pre- and post-test scores can be categorized into three groups as no change, lower

post-test score and higher post-test score and compared through the Chi-Square test between intervention and control to assess whether the increase or decrease in the post-test score is differing among the two groups.

Next, to assess the effect of the study condition, there are three adequate ways to analyse a numerical outcome (GAD-7, EPDS and R-DAS) where the common point of these approaches is that the prescores must be considered (the best approach will be chosen accordingly):

- 1. Independent samples-test on change of scores (i.e., the post-minus-pre differences), assuming the normality assumption is satisfied. The overall test is statistically significant if it yields a sufficiently small p-value. Following the hypothesis testing, the Cohen's d effect size statistic will be calculated for intervention effects. If a nonparametric approach is chosen (assuming normality assumption is deviated), the Mann-Whitney test should be performed on change scores. The effect size for the Mann-Whitney U test is calculated by dividing the standardised test statistic z and square root of the number of pairs n.
- 2. Two-way mixed-model ANOVA with group as between-subjects factor (intervention and control groups) and time-point as within-subject factor (i.e., repeated measures; with two levels, baseline, and post-intervention). Note that the p-value for interaction in this design will be equivalent to the p-value from the independent samples t-test on change scores mentioned in (1). This will also answer the essential question of the study: do the changes from baseline differ between the groups?
- 3. Analysis of covariance (ANCOVA) of post-intervention scores with baseline score as the covariate. This approach differs subtly from the two mentioned above. Analysis of covariance treats the pre-test value as a covariate that can be a source of variation that may influence post-test scores, and accordingly the post-test score is regressed on both the pre-test score and the grouping variable. ANCOVA adjusts the pre-test scores, increasing the power to determine whether or not there has been a treatment effect. This approach tests the null hypothesis of no difference between the control and treatment post.

Should the results indicate that there has been significant improvement at post-testing, one should also evaluate for any differences in the change of scores between the two groups through stepwise linear regression using a bootstrapping procedure with 5000 replications recommended for analyses with smaller sample sizes (Preacher and Hayes, 2008). Groups alone will be included in Model 1, and any confounds that differed across the two groups at baseline will be included in Model 2, allowing for the comparison of the effect size as a function of study condition in unadjusted and adjusted models. Results will be determined to be statistically significant if p values were <0.05.

Furthermore, it would be of interest to see whether there is an association between a high score in ANRQ and the incidence of depression and anxiety. Thus, the idea is to check for any possible correlation between ANRQ and EPDS and ANRQ and GAD-7 for both pre- and post-testing, through the Pearson correlation or alternatively the Spearman correlation, if the assumption of normality is not satisfied.

The assumption of normality to perform all the above tests will be evaluated by the Shapiro-Francia test. If the assumption of normality has been violated, the p-value will be less than 0.05. If the assumption of normality has not been violated, the p-value will be greater than 0.05. This is because the Shapiro-Wilk test is evaluating the null hypothesis that the distribution of the data is equal to a normal distribution. Rejecting the null hypothesis means that the distribution of the data is not equal to a normal distribution.

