#### Randomisation

Participants will be randomly assigned using a computer-generated sequence to one of the two study arm groups, that is the intervention group or the control group. These randomly generated treatment allocations will be placed in sequentially numbered opaque, sealed envelopes. Therefore, once a participant consents to enter the study, an envelope will be opened by the clinician and the participant mother will be offered the allocated treatment regime. The statistician responsible for generating the randomisation sequence will not be responsible for recruiting participants and will not be administering it. Altogether these processes will ensure that each participant has an equal chance of being assigned to any of the two groups and that the investigator cannot predict in which group each participant will be assigned to (Cochrane, 2013).

Mothers who withdraw from treatment after the randomization would have taken place would still be included in the intervention and control groups respectively according to how they would have been assigned to mitigate intervention effect bias (McCoy, 2017). The Intention To Treat Principle (ITT) will be applied, to reduce the risk of intervention bias.

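### Covariates for the adjusted follow-up model are chosen by testing the randomised arms for baseline differences, so they reflect chance imbalance and not prognosis, and precision is lost

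*Protocol*

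**What the plan says.** All of this is in the protocol; no statistical analysis plan is at hand.

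- **Allocation** (Randomisation): "Participants will be randomly assigned using a computer-generated sequence to one of the two study arm groups".
- **Selection rule** (Analytic Methods): demographics are compared between arms by binomial logistic regression. The rule reads: "Any baseline demographic factor that differed between the two groups at p < 0.10 will be included as a potentially confounding variable". The models meant are the later ones that estimate the treatment effect.
- **Fallback** (same paragraph): if the data are too sparse for that, "alternatively, a Chi-Square test of association will be carried out by selected demographic variables". The null hypothesis of that test "will be accepted if the p-value exceeds the 0.05 level of significance". The paragraph does not say whether this level also decides inclusion.
- **Where the rule lands** (Analytic Methods, after the three candidate analyses): if there has been significant improvement, the change in scores is analysed by a bootstrapped stepwise linear regression. Model 1 holds the group term only. For the adjusted model, "any confounds that differed across the two groups at baseline will be included in Model 2". The two effect sizes are to be compared, at a significance level of 0.05.

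No demographic covariate is named in advance, and predicting the outcome is not a condition for entry.

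**The concern.** A covariate earns its place in a randomised comparison by predicting the outcome. A test of the arms against each other at baseline measures something else: how far chance happened to separate them. A factor unrelated to EPDS, GAD-7 or R-DAS is as likely to be flagged as a strong predictor, and a strong predictor that happens to be balanced is left out, although adjusting for it would narrow the confidence interval.

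Three further weaknesses follow from the text:

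- Model 2 cannot be written down until the baseline data have been tested, yet the plan reads meaning into the difference between Models 1 and 2.
- Model 2 is fitted to change scores and adds only factors that differed, so the baseline score, probably the best single predictor, is not a covariate.
- A factor with p = 0.07 enters by the logistic route. By the chi-square route its status is unclear. With 30 per arm, a non-significant test is in any case not evidence of balance.

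At stake are the precision of the adjusted estimate and whether it can be read as a pre-planned result.

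**Working it through.** The protocol gives no power, effect size or error rate tied to this rule, so there is no stated figure to reproduce. What follows is illustration.

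**Inputs from the protocol:** 60 mothers, 30 per arm (Trial Design; Trial Flow Chart); inclusion at p < 0.10; chi-square decision level 0.05; results judged at 0.05.

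**Assumed, because not given:** number of factors k, their independence, their correlation with the outcome, the treatment effect, and the pre-post correlation ρ.

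**Step 1. How often chance flags something.** For k independent factors tested at level a, P(at least one flag) = 1 − (1 − a)^k, and the expected number of flags is k × a.

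| k | expected at 0.10 | P at 0.10 | P at 0.05 |
|---|---|---|---|
| 3 | 0.3 | 1 − 0.9³ = 27% | 1 − 0.95³ = 14% |
| 5 | 0.5 | 1 − 0.9⁵ = 41% | 1 − 0.95⁵ = 23% |
| 8 | 0.8 | 1 − 0.9⁸ = 57% | 1 − 0.95⁸ = 34% |
| 10 | 1.0 | 1 − 0.9¹⁰ = 65% | 1 − 0.95¹⁰ = 40% |

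The last two columns also show how much the content of Model 2 depends on which threshold is meant.

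**Step 2. Whether selection tracks prognosis.** In a simulation of 10,000 trials per setting (30 per arm, six factors, one prognostic with correlation 0.3, 0.5 or 0.7 with the outcome), the prognostic factor was selected 9.2% to 10.1% of the time. That is the nominal 10%, whatever its strength.

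**Step 3. Cost in power.** Simulation of 4,000 trials per setting: 30 per arm, effect 0.5 SD, eight factors, two of them with r = 0.3 with the post score and independent of the baseline score.

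| Outcome model | Covariates | ρ = 0.4 | ρ = 0.6 |
|---|---|---|---|
| Change score | none | 0.41 | 0.57 |
| Change score | selected at p < 0.10 | 0.40 | 0.56 |
| Change score | the two, pre-set | 0.46 | 0.65 |
| ANCOVA on baseline | none | 0.53 | 0.66 |
| ANCOVA on baseline | selected at p < 0.10 | 0.53 | 0.66 |
| ANCOVA on baseline | the two, pre-set | 0.62 | 0.78 |

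- Selected against pre-set, change score: 0.46 − 0.40 = 6 points and 0.65 − 0.56 = 9 points.
- Selected against pre-set, ANCOVA: 0.62 − 0.53 = 9 points and 0.78 − 0.66 = 12 points.
- Selected against no covariates: no gain in either model (0 to 1 point lower).
- Change score against ANCOVA, selected covariates in both: 0.53 − 0.40 = 13 points and 0.66 − 0.56 = 10 points.

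The last line agrees with theory. With unit variances the change score has variance 2(1 − ρ), which is 1.20 or 0.80. The ANCOVA residual variance is 1 − ρ², which is 0.84 or 0.64.

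**Step 4. Type I error.** Under the selection rule it was 0.040 to 0.049 in the Step 3 setting. In the Step 2 setting it was 0.046, 0.040 and 0.029 for prognostic correlations of 0.3, 0.5 and 0.7. The rule is mildly conservative.

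These simulations used ordinary least squares and t-tests at baseline, not the plan's bootstrap and logistic regression.

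**The case against.** The best defence is scope. The protocol offers three ways to assess the effect of study condition: a test on change scores, a mixed ANOVA, and ANCOVA with the baseline score. All take account of the pre-score, and none states the p < 0.10 rule. The rule is explicitly carried only into Model 2 of a regression that is run conditionally and shown beside the unadjusted Model 1. Read that way, it works much like a sensitivity analysis. This stands. It limits the point to Model 2 and lowers its severity, but it does not make the rule a sound way to choose covariates.

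Four stronger readings are tempting, and the documents do not support them:

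- **That the rule inflates false positives.** Step 4 shows the opposite, slight conservatism.
- **That the main comparison is compromised.** The three candidate analyses do not use the rule.
- **That the rule alone costs over 20 points of power.** Going from 0.40 to 0.62, or from 0.56 to 0.78, changes two things at once: the way covariates are chosen and the outcome model. Only 6 to 12 points belong to the covariate rule, and ANCOVA is already one of the plan's options.
- **That 0.10 and 0.05 contradict each other.** The 0.05 sentence gives the decision level of the chi-square test and is silent on inclusion. The text is ambiguous, not contradictory.

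The size also depends on assumptions. If the two prognostic factors correlate 0.3 with the baseline score as well, pre-set covariates gain only about 1 point over selected ones in the change model and 3 to 5 in ANCOVA.

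**Conclusion.** The concern holds for Model 2 of the follow-up regression. The protocol fixes a concrete rule that selects chance imbalances without regard to prognosis, leaves the adjusted model undefined until the data are seen, and omits the baseline score as a covariate. It is also unclear which threshold defines a difference in the fallback.

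The harm is forgone precision: about 6 to 12 points of power from selecting rather than pre-setting covariates, and about 10 to 13 more from using change scores. Both figures assume a 0.5 SD effect, pre-post correlation 0.4 to 0.6, and two prognostic factors with r = 0.3 that are independent of the baseline score. If those factors also correlate with the baseline score, the first figure shrinks. That selection is blind to prognosis needs only correct random allocation.

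Severity: should be fixed.

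**What to change.** 1. Remove baseline significance tests as a way of choosing covariates, by both the logistic and the chi-square route, and describe baseline data by arm without p-values. This also removes the threshold ambiguity.
2. Before outcome data are analysed, define Model 2 as post score on group, baseline score of the same outcome, and one or two named prognostic variables that the protocol already records. Examples are the ANRQ score (Phase II assessment, before randomisation) and recruitment route (booking-visit screening or referral to the Perinatal Mental Health Service).
3. Enter these terms together, not stepwise, with the same specification for EPDS, GAD-7 and R-DAS.
4. Keep the unadjusted model alongside, for comparison.

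**Cost:** wording only, with no new data collection for the variables named. The downside is one or two degrees of freedom at n = 60 if a named covariate proves not to be prognostic.

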# **Trial Design**

A two-group design is appropriate:

Those mothers who score above the cut-off point on the EPDS and the GAD 7 with depression or anxiety will receive psychiatric assessment plus medication (if needed) plus a monthly phone call by a midwife, plus 12 sessions of systemic therapy in the **Intervention Group** 

And a psychiatric assessment plus medication (if needed) plus a monthly phone call by a midwife in the **Control Group** 

The outcomes

AN Mothers who score above the cut-off point on the EPDS and the GAD 7

with anxiety and depression in the Intervention Group will have a better outcome reflected through:

- (i) a lower and statistically significant score on the EPDS and GAD7 when compared to those in the control group
- (ii) a higher statistically significant score on the Dyadic Adjustment Scale Revised (R-DAS) when compared to those in the Control Group

The allocation ratio is intended to be as follows:

**60 mothers**; (30 ANmothers will be in the intervention group, whereas **30**ANmothers will be in the control group)

During the screening process, AN mothers who score above the cutoff point in the EPDS and the GAD7 will be put in one cluster. The randomisation into the intervention and the control group will take place through the process described below.

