# TRIAL FLOW CHART – ( Mental Health Cluster) ANTENATAL MOTHERS

At antenatal period (after 12 weeks pregnancy during first booking visit), a batch of 100 mothers who happen to have the booking appointment at the time of distribution of the screening sheets are asked to complete the Phase I assessment including brief Demographic Data, Whooley Questions & Relationship Questions. Screening sheets sent by post prior to first booking appointment.

Mothers with no Mental Health Difficulties receive treatment as usual from Gynae and Obs. Mothers with Mental Health Difficulties are asked by the recruiter, normally a midwife to complete Phase II assessment (including EPDS, GAD7, R-DAS, ANRQ). Those scoring for anxiety and/or depression are assessed through the MINI for a diagnosis by psychiatrist/clinical psychologist making use of the MINI

Antenatal mothers who are diagnosed with anxiety or depression and are willing to participate in the RCT, will form part of the Mental Health Cluster of this study. 60 mothers will be randomised:

- a. 30 in intervention group
- b. 30 in control group

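### The therapy effect is judged by p-value through an unfixed choice of analysis and a test-dependent effect size, with no planned statement of what a non-significant result in 60 mothers leaves open

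*Protocol*

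**What the plan says.** **Size.** The flow chart states that "60 mothers will be randomised", with "30 in intervention group" and the same number in control. Trial Design introduces these numbers with "The allocation ratio is intended to be as follows". No power, target difference, SD or dropout accompanies them.

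**Definition of benefit.** Trial Design describes the better outcome as a statistically significant advantage over control: lower on EPDS and GAD-7, higher on R-DAS.

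**Analysis of the three scales (Analytic Methods).** Three approaches are listed, and the best is to be chosen:

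- An independent-samples test on change scores, judged by its p-value: "The overall test is statistically significant if it yields a sufficiently small p-value". For the size of the effect under this option, the plan adds one line: "Following the hypothesis testing, the Cohen's d effect size statistic will be calculated for intervention effects". If normality fails, Mann-Whitney is used instead, with an effect size of z over root n.
- A two-way mixed ANOVA, with no effect measure named.
- ANCOVA of the post score on baseline, with no effect measure named.

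A bootstrapped regression of change scores then compares the group effect without and with adjustment for confounders. It is run only if there has been a significant improvement. The section closes its threshold rule with "Results will be determined to be statistically significant if p values were <0.05".

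**Baseline comparison (same section).** If logistic regression is not feasible, "a Chi-Square test of association will be carried out by selected demographic variables to see whether the two groups showed any demographic differences", and the null hypothesis "will be accepted if the p-value exceeds the 0.05 level of significance".

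Confidence intervals appear only for the test-retest reliability coefficients.

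**The concern.** A trial of 60 can easily return p>0.05 when therapy has a moderate effect. What then matters is how large a benefit the data still allow. The written rules do not lead there: benefit is defined by significance, and the outcome rules give only a threshold. The one analysis that sets unadjusted and adjusted effects side by side is withheld unless something was significant, so a null result gets the least estimation.

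The open choice adds to this. One scale could be summarised by d, another by z over root n, and a third by an F-test with no effect measure. These are not on a common footing, and neither d nor z over root n is in points on the questionnaire. The trial is meant to show whether systemic therapists can help these mothers, and that needs a difference in points with its uncertainty.

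**Working it through.** The Protocol's figure of 60 cannot be reproduced, because it gives nothing from which to derive it. The check is therefore of what 30 per arm can show.

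**Inputs.** From the Protocol: n = 30 per arm and a 0.05 threshold. Assumed: a two-sided test (sidedness is not stated), everyone analysed unless noted, pre-post correlation ρ of 0.3 to 0.7, and an SD of 4 to 6 points for illustration.

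**Power.** This is a plain two-sample t-test with df = 58 and noncentrality d·√(n/2), where d is in SDs of the variable analysed.

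| d | Power, 30 per arm |
|---|---|
| 0.3 | 0.21 |
| 0.5 | 0.48 |
| 0.8 | 0.86 |

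A true 0.5 SD effect is therefore missed with probability 1 − 0.48 = 0.52. Power of 80% needs d of about 0.74. With 27 or 24 per arm analysed, power at d = 0.5 falls to 0.44 or 0.40.

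**Half-width of the 95% CI, in SDs of the score.** √(2/30) = 0.258.

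- Change scores: t(58)·√(2/30)·√(2(1−ρ)), where 2.002 × 0.258 = 0.517.
- ANCOVA: t(57)·√(2/30)·√(1−ρ²), where 2.002 × 0.258 = 0.517.

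| ρ | Change scores | ANCOVA |
|---|---|---|
| 0.3 | 0.517 × 1.183 = 0.61 | 0.517 × 0.954 = 0.49 |
| 0.5 | 0.517 × 1.000 = 0.52 | 0.517 × 0.866 = 0.45 |
| 0.7 | 0.517 × 0.775 = 0.40 | 0.517 × 0.714 = 0.37 |

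ANCOVA is narrower at each correlation. In points, its half-width runs from 0.37 × 4 = 1.5 to 0.49 × 6 = 2.9. Change scores run from 0.40 × 4 = 1.6 to 0.61 × 6 = 3.7. An observed difference of zero would thus leave roughly 0.4 to 0.6 SD unexcluded in either direction, depending on method and correlation.

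**Effect-size metric.** The Protocol does not say what d is divided by. If it is the SD of change, d equals the raw-SD d times 1/√(2(1−ρ)): 0.85, 1.00 or 1.29 at ρ = 0.3, 0.5 or 0.7. For Mann-Whitney, n is described as a number of pairs although the arms are independent. Taking n as 30 instead of 60 multiplies the result by √2 = 1.41.

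**The baseline chi-square.** With 30 per arm, power to detect 50% against 30% is about 0.35 (normal approximation), so accepting no association on p>0.05 is unsound there too.

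**The case against.** Several points on the other side stand.

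- **Reach of the acceptance rule.** A reader might infer that the Protocol tells the trial to conclude that therapy makes no difference when p>0.05. It does not. The sentence belongs to the fallback chi-square on demographics. The outcome paragraphs say when a result is significant and are silent on what follows otherwise. A chi-square on change categories is also offered for the outcomes, but the rule is not repeated there, and carrying it across would be a guess.
- **Other outputs.** A reader might also infer that p-values and effect sizes are all that will be reported. That is too strong. Means, medians and SDs by arm before and after treatment are planned, with boxplots and the conditional regression. ANCOVA is already a listed option, and its group coefficient is the difference wanted.
- **The missing interval.** Taken alone, this could be left to an analysis plan that is not at hand. So could the divisor for d, and using d after a t-test and z over root n after Mann-Whitney is common practice.
- **Power.** The figures describe a trial of 60, and better reporting does not change them.

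This does not dispose of the written rules: benefit defined by significance, an analysis left open, and an effect comparison made conditional on significance. A later plan would have to correct these, not merely fill them in. The power figure shows why they matter at this size; it is not offered as a separate fault.

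**Conclusion.** The point holds in a limited form. The Protocol ties the therapy result to p-values, leaves the analysis and the effect metric to a later choice, and makes the adjusted/unadjusted comparison depend on significance. With 30 per arm, a true 0.5 SD benefit would give p>0.05 about half the time, and no statement is planned of what such a result fails to exclude.

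The documents do not support saying that the trial will declare therapy ineffective on p>0.05, or that nothing but p-values will be reported. The *accepted* wording is a minor error confined to the baseline comparison.

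The 0.48 assumes a two-sided plain t-test with all 60 analysed. The half-widths rest on assumed correlations of 0.3 to 0.7, and the values in points on an assumed SD of 4 to 6. The case for ANCOVA over change scores does not hang on one correlation: it gives the narrower interval across the range shown.

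**What to change.** In Analytic Methods:

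1. Replace the open choice with one stated result for each of EPDS, GAD-7 and R-DAS: the ANCOVA baseline-adjusted between-arm mean difference in scale points with its 95% CI, reported whatever the p-value.
2. Remove the condition that a significant improvement must come before the unadjusted and adjusted effects are compared.
3. State that p>0.05 will not be described as showing no effect, and that the interval will be used to say what remains possible.
4. Minor: in the baseline chi-square sentence, change *accepted* to *not rejected*.

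Naming in advance a difference worth excluding, and fixing one divisor for d, would help but are optional and can sit in the analysis plan.

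No new data, visits or participants are needed, and the estimate and interval come from a model already listed. Item 1 is more than rewording, since it settles which analysis counts, so it should be made before outcomes are seen by arm.
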